### 3.7.2 Secondary Efficacy Analyses

#### 3.7.2.1 Cervical mucus protection in each type of treatment period

The aim of this secondary objective is to assess the level of cervical mucus protection during reported perfect use, during a treatment period with a delayed pill intake of 6 hours and during a treatment period with a missed pill of norgestrel 75 mcg. The FASM population will be used for the analysis and a sensitivity analysis will be done using ITT and PP.

The time frames are:

- reported perfect use: all the visits of the period 1
- delayed pill intake: all the visits of the period 2 for Arm A and all the visits of period 3 for Arm B.
- missed pill: all the visits of the period 2 for Arm B and all the visits of period 3 for Arm A.

The assessment criterion is the cervical mucus score. The cut off is a cervical mucus score of 4. There is conception protection by cervical mucus if the cervical mucus score is  $\leq 4$ .

The endpoints are:

- The percentage of subjects with cervical mucus score  $\leq 4$ , between 5 and 8, and  $\geq 9$  in reported perfect use period
- The percentage of subjects with cervical mucus score  $\leq 4$ , between 5 and 8, and  $\geq 9$  in delayed pill intake periods
- The percentage of subjects with cervical mucus score  $\leq 4$ , between 5 and 8, and  $\geq 9$  in missed pill periods
- The percentage of subjects with cervical mucus score  $\leq 4$  in all periods

If the cervical mucus was too thick to be collected (and thus a cervical mucus score could not be obtained) the analysis will consider the sample to have good contraception protection and have a cervical mucus score  $\leq 4$ . Otherwise if the cervical mucus score is missing the subject will not be included in the analysis. A period must have at least 7 cervical mucus assessment to be included in the summaries. A stratified McNemar test (stratification on the site, CMH option in SAS) will be used to compare the distribution of cervical mucus scores in the perfect use period to the delayed and missed pill periods (pairwise vs perfect use).

The worst (meaning highest) cervical mucus score in the period will be used for the analyses.

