## **5.0 APPENDICES**

### 5.1 Schedule of Assessments

Study periods	Screening visit	Treatment phase										Follow up(a)	End of study visit
		Treatment period 1	Treatment period 2				Treatment period 3						
Days	-	D1 to D28	D29 to D56				D57 to D84				D85 to D96	Between D85 and D100	
		D1 to D28	D29 to D40 ±3 And D44±3 to D56	D41±3 to D43±3		D57 to D68 ±3 And D72±3 to D84	D69±3 to D71±3						
Visits	V0	V1 1 to V1 2	V2 1 to V2 4				V3 1 to V3 4				V4 1 to V4 2	V4 3	
		Visits twice a week if follicle < 15 mm Visits every other day for a maximum of 6 days if a growing follicle ≥ 15 mm identified upon TVUS(b)	Visits twice a week if follicle < 15 mm Visits every other day for a maximum of 6 days if a growing follicle ≥ 15 mm identified upon TVUS(b)	Delayed/missed pill period Three consecutive days		Visits twice a week if follicle < 15 mm Visits every other day for a maximum of 6 days if a growing follicle ≥ 15 mm identified upon TVUS(b)	Delayed/missed pill period Three consecutive days			Visits every other day for a maximum of 12 days if a growing follicle ≥ 15 mm identified upon TVUS(c)			
				V2 1A	V2 1B	V2 1C		V3 1A	V3 1B	V3 1C			
Informed consent	X												
Inclusion/exclusion criteria	X	X											
Randomisation			X(d)										
Demographics	X												
Medical, surgical and gynecological history	X												
Physical & gynecological examination	X												
Vital signs(e)	X										X		
Laboratory tests	X										X		
Pap smear(f)	X												
STI screening	X												
High-sensitivity urine pregnancy test (β-HCG)		X(g)									X		
Dispensation of study medication (h)		X	X										

Study periods	Screening visit	Treatment phase										Follow up(a)	End of study visit	
		Treatment period 1	Treatment period 2				Treatment period 3							
Days	-	D1 to D28	D29 to D56				D57 to D84				D85 to D96	Between D85 and D100		
		D1 to D28	D29 to D40 ±3 And D44±3 to D56	D41±3 to D43±3		D57 to D68 ±3 And D72±3 to D84		D69±3 to D71±3						
Visits	V0	V1, to V1 y	V2, to V2 y				V3, to V3 y				V4, to V4 y	V4 y		

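### The 7-assessment minimum in SAP 3.7.2.1 lets a delayed- or missed-pill period count as protected although mucus was never scored on the day of the infringement

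*SAP*

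**What the plan says.** Section 3.7.2.1 estimates the share of women with protective mucus in three kinds of period: perfect use (period 1), delayed pill and missed pill. Four rules matter here.

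- **Time frame.** The whole 28-day period counts, for example "missed pill: all the visits of the period 2 for Arm B and all the visits of period 3 for Arm A".
- **Classification.** "The worst (meaning highest) cervical mucus score in the period will be used for the analyses", and "The cut off is a cervical mucus score of 4".
- **Inclusion.** "A period must have at least 7 cervical mucus assessment to be included in the summaries". No particular day is required.
- **Missing scores.** Mucus too thick to collect is treated as protective. For other missing scores, "Otherwise if the cervical mucus score is missing the subject will not be included in the analysis".

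The schedule in section 5.1 sets the number of visits. Outside the delayed/missed pill (DMP) days it gives "Visits twice a week if follicle < 15 mm", which in period 2 covers "D29 to D40 ±3 And D44±3 to D56". Three consecutive DMP visits (R-1, R and R+1) are added. A growing follicle brings further visits: "Visits every other day for a maximum of 6 days if a growing follicle ≥ 15 mm identified upon TVUS".

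**The concern.** A delayed- or missed-pill period is meant to show what happens to mucus when a pill is late or omitted. A count of seven with no condition on days can be met entirely by ordinary twice-weekly visits away from the infringement. A woman sampled that way, with every score at 4 or below, enters the delayed- or missed-pill percentage as protected although nobody looked at her mucus at the time in question. Because the summary is a maximum, leaving samples out can lower it or leave it unchanged, but can never raise it. For an admitted period the error therefore goes one way, towards protection. At stake is whether these two percentages, and their McNemar comparisons with period 1, answer the question that section 3.7.2.1 sets.

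**Working it through.** The SAP gives no derivation for the threshold of seven, so there is no plan figure to reproduce. The check is a visit count, followed by an illustration of size.

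**Step 1: planned assessments (section 5.1)**

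- Period 2 outside the DMP days: D29 to D40 is 12 days and D44 to D56 is 13 days, 25 in all. Period 3 (D57 to D68, D72 to D84) also gives 12 + 13 = 25.
- At two visits a week: 25 × 2/7 = 7.1, so about 7 ordinary visits. With 3 DMP visits the total is about 10.
- If the DMP visits replace ordinary ones, the total falls to 5 + 3 = 8.
- The ±3-day windows make 6 or 8 ordinary visits possible as well.

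**Step 2: which patterns still reach seven**

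| Ordinary visits | Planned total | Only R missing | R and R+1 missing | All three DMP visits missing |
|---|---|---|---|---|
| 5 | 8 | 7, admitted | 6, excluded | 5, excluded |
| 6 | 9 | 8, admitted | 7, admitted | 6, excluded |
| 7 | 10 | 9, admitted | 8, admitted | 7, admitted |
| 8 | 11 | 10, admitted | 9, admitted | 8, admitted |

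A period without the day-R sample is admitted in every row. One without R and R+1 is admitted from 6 ordinary visits upward, and one with no DMP sample from 7 upward. Extra follicle visits can lift the excluded cells over the threshold.

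**Step 3: size**

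One misclassified woman among 45 completers (section 2.5) moves a percentage by 1/45 = 2.2 points. That applies only if her unobserved score exceeded 4 while all her observed scores did not.

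The SAP gives no rate of missed R or R+1 samples and no chance of a raised score. As an illustration, assume a probability π of 10% to 30% that the score exceeds 4 at R or R+1, a probability q of 1% to 5% at each of the other 8 visits (7 ordinary plus R-1), and independent visits.

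- With R and R+1 sampled, P(classed as not protected) = 1 − (1 − π)(1 − q)^8.
- Without them, it is 1 − (1 − q)^8.
- The gap is π(1 − q)^8.

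| π | q | With R, R+1 | Without | Gap |
|---|---|---|---|---|
| 10% | 1% | 17.0% | 7.7% | 0.10 × 0.923 = 9.2 points |
| 30% | 1% | 35.4% | 7.7% | 0.30 × 0.923 = 27.7 points |
| 10% | 5% | 40.3% | 33.7% | 0.10 × 0.663 = 6.6 points |
| 30% | 5% | 53.6% | 33.7% | 0.30 × 0.663 = 19.9 points |

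The shift in the reported percentage is the gap times the share of admitted periods that lack both samples. If that share were 10% (assumed), the shift would be 0.7 to 2.8 points. At 20% (assumed) it would be 1.3 to 5.5 points. The planning difference in section 2.5 is 14 to 15 points.

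**The case against.** The strongest reply is that this endpoint deliberately covers the whole 28-day period. The acute effect at R and R+1 belongs to the primary mixed model and the subordinate McNemar analysis in section 3.7.1, both built on the DMP scores, and the study is exploratory. That is right and limits the consequence to one secondary analysis. It does not justify labelling a period by an infringement at which mucus was not scored.

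There are also safeguards. The full analysis sets rest on data complete enough for an adjudication committee to judge each cycle, and that committee decides exclusions blinded (sections 3.4 and 5.2). Its charter is not at hand and may require DMP samples. The per-protocol set needs complete mucus data in all three periods and is already a planned sensitivity analysis here. These reduce the risk, but the SAP writes no DMP-sample condition for the main analysis, and the FASM asks only for mucus information in period 2 or 3.

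Three stronger readings are tempting, and the document does not support them.

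- **Excluding short periods hides failures.** One score above 4 among six samples does settle that the period was not protected, and the rule still drops it. But it also drops six-sample periods with every score at 4 or below. If missed visits are unrelated to score, this does not bias the percentage in itself, and nothing in the SAP shows that short periods contain more failures.
- **The rules together favour protection in the comparison with perfect use.** The net direction is not determined. Dropping short period-1 records that show loss would flatter perfect use, and extra follicle visits would, if anything, ease the inclusion of women with more ovarian activity.
- **The missing-score sentence contradicts the minimum of seven.** It can refer to the single period score that is analysed, with the next sentence stating when a period counts. It is ambiguous rather than contradictory.

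**Conclusion.** The point holds as a gap in the inclusion rule of one secondary analysis. A delayed- or missed-pill period without a day-R score is admitted on every reading of the schedule. On the roughly 10-visit reading, one with no DMP score at all is admitted too. Either can be reported as protected. For the periods concerned the error can only overstate protection, because a maximum cannot rise when samples are left out.

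The overall size is unknown. It is about 2.2 points per misclassified woman at n=45, and the shifts in the working rest on assumed score probabilities, independent visits and an assumed share of periods lacking both samples. The visit count is inferred from section 5.1. On the 8-visit reading only the loss of R alone passes, unless extra visits occur. The primary model is untouched.

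**What to change.** Keep the minimum of seven in section 3.7.2.1. Add that a delayed- or missed-pill period is included only if the samples on day R and day R+1 were both assessed, that mucus too thick to collect counts as assessed, and that the condition applies whatever scores were observed.

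Do not rescue short periods because they contain a score above 4, since that makes inclusion depend on the outcome. To illustrate, assume a 5% chance of a score above 4 at each visit, 10 visits in a full period, 6 in a short one, and missed visits unrelated to score.

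- Full periods show loss in 1 − 0.95^10 = 40.1%, and short ones in 1 − 0.95^6 = 26.5%.
- With 10% short periods, keeping only those with loss gives (0.9 × 0.401 + 0.1 × 0.265) / (0.9 + 0.1 × 0.265) = 41.8%.
- With 20% short periods, the same calculation gives 43.8%.

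If short periods are a worry, show at most a sensitivity analysis with bounds: all short periods counted as protected, then all counted as not protected.

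The cost is one added sentence and a derivation flag before analysis. A few periods without R or R+1 samples leave the summary, including any with a raised score at another visit, and those women drop out of the affected pairwise comparison with period 1.

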- (m) At V11, the mucus analysis will be performed before the 1st study medication intake
- (n) Mucus analysis to be performed at T2/3R-1 +8 h ± 30 min.
- (o) Mucus analysis to be performed at T2/3TR-1 +3h ± 15 min.
- (p) Mucus analysis to be performed at T2/3R-1 +6 h ± 15 min.
- (q) Mucus analysis to be performed within 30 min before study medication intake
- (r) Blood sampling for PK analysis at D1: subjects with even study number at predose, 2 h ± 15 min, 6 h ± 15 min and 12 h ± 30 min post-treatment and subjects with odd study number at 1 h ± 15 min, 4 h ± 15 min , 8 h ± 30 min and 24 h ± 30 min post-treatment

- (s) Blood sampling for steady state during first visit in week 3: subjects with odd numbers at predose, and between 0.5 h and 2h (morning visit), and subject with even numbers between 5 h and 9 h post-treatment (afternoon visit)
- (t) Blood sampling for compliance during 1st visit of weeks 5 and 9 within 30 min of cervical mucus sampling
- (u) Blood sampling for PK analysis at  $T2/3_{R-1} + 8h \pm 30 \text{ min}$
- (v) Blood sampling for PK analysis at  $T2/3_{R-1} + 3h \pm 15 \text{ min}$ ,  $T2/3_{R-1} + 5.5h \pm 15\text{min}$ ,  $T2/3_{R-1} + 7.5h \pm 30\text{min}$
- (w) Blood sampling for PK analysis at  $T2/3_{R-1} + 6h \pm 15\text{min}$
- (x) Blood sampling for PK analysis at  $T2/3_{R-1}$  within 30 min before study medication intake
- (y) No E2, FSH and LH measurements during extra-visits after postovulatory image is observed

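### The worst-score comparison with perfect use rests on unequal sample counts (about 8 in period 1, one of them pre-dose, against about 10), so it is biased in an unknown direction

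*SAP*

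**What the plan says.** SAP Section 3.7.2.1 reduces each period to one value per woman: "The worst (meaning highest) cervical mucus score in the period will be used for the analyses". The windows are whole periods. Perfect use is defined as "reported perfect use: all the visits of the period 1". The delayed-pill window is "delayed pill intake: all the visits of the period 2 for Arm A and all the visits of period 3 for Arm B", and the missed-pill window mirrors it. A site-stratified McNemar test compares each infringement period with perfect use. A period needs at least 7 mucus assessments to enter. That is a floor only, with no upper limit and no matching of counts between periods.

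The schedule in Section 5.1 has the same regular rule in all three periods: "Visits twice a week if follicle < 15 mm". Period 2 has its regular visits on "D29 to D40 ±3 And D44±3 to D56", and between these blocks a "Delayed/missed pill period Three consecutive days". Period 3 has the same layout. Footnotes (n) to (q) put a mucus analysis on each of those three days. Footnote (m) says of the first period 1 visit, V1_1, that "the mucus analysis will be performed before the 1 st study medication intake".

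**The concern.** The McNemar test asks whether the proportion of women whose worst score exceeds 4 is the same in two periods. If a woman has the same chance of a high score at every sample, she is still more likely to show at least one high score in 10 samples than in 8. The null hypothesis is then false because of the visit schedule alone. One of the three added days, R-1, comes before the infringement (Section 3.7.1), so it cannot show an effect of it, yet it counts towards the worst score of the infringement period.

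A second distortion sits in period 1. The V1_1 sample is untreated mucus, but the window counts it as perfect use. Under a worst-score rule, that single sample can fix the woman's value for the whole period.

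Comparing perfect use with each infringement period is a stated secondary objective (Section 2.2). A significant difference, or the lack of one, could be read as evidence on missed or delayed pills when it reflects sample counts and one untreated sample.

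**Working it through.** The SAP states no sample count per period and no per-sample rate, so there is no figure of its own to reproduce on this point.

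**Sample counts (Section 5.1, two visits a week, no extra visits).**
- Period 1: 28/7 × 2 = 8, of which V1_1 is pre-dose, leaving 7 on drug.
- Periods 2 and 3: regular days 12 + 13 = 25, so 25/7 × 2 = 7.1; plus 3 delayed/missed-pill days = 10.1, about 10 (9 to 11 depending on how visits fall).

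**Excess with no infringement effect.** Let p be the chance that one on-drug sample scores above 4, the same in all periods. With independent samples, P(worst score above 4 in k samples) = 1 − (1 − p)^k. With within-woman correlation ρ, the beta-binomial form is 1 − Π (b + i)/(a + b + i) for i = 0 to k − 1, where a = p(1 − ρ)/ρ and b = (1 − p)(1 − ρ)/ρ. Both p and ρ are assumed.

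| p | ρ | k = 7 | k = 8 | k = 10 | 10 minus 8 | 10 minus 7 |
|---|---|---|---|---|---|---|
| 5% | 0 | 30.2% | 33.7% | 40.1% | 6.5 | 10.0 |
| 5% | 0.1 | 24.1% | 26.2% | 30.0% | 3.7 | 5.9 |
| 5% | 0.2 | 20.0% | 21.4% | 23.9% | 2.5 | 4.0 |
| 10% | 0 | 52.2% | 57.0% | 65.1% | 8.2 | 13.0 |
| 10% | 0.1 | 43.1% | 46.3% | 51.6% | 5.4 | 8.6 |
| 10% | 0.2 | 36.5% | 38.8% | 42.7% | 3.9 | 6.2 |

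The last two columns are percentage points, taken from unrounded values. The 8 versus 10 column treats V1_1 as if it were an on-drug sample; the 7 versus 10 column leaves it out.

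**False-positive rate.** Simulated two-sided McNemar test at the 5% level, 45 women, unstratified, score split at 4, p = 5-10%, ρ = 0.1-0.2:
- 8 versus 8: about 1.5 to 3% (exact).
- 8 versus 10: about 2.5 to 6% (exact), about 6 to 9% (asymptotic).
- 7 versus 10: about 4 to 11% (exact), about 9 to 16% (asymptotic).

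Section 3.7.2.1 names the CMH option and does not ask for an exact test, so the asymptotic figures are the nearer guide.

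**Effect of the pre-dose sample.** Let q be the chance that the untreated V1_1 sample scores above 4. With independent samples, period 1 then has P = 1 − (1 − q)(1 − p)^7, against 1 − (1 − p)^10 in an infringement period. These are equal when q = 1 − (1 − p)^3:
- p = 5%: 1 − 0.95³ = 14.3%.
- p = 10%: 1 − 0.90³ = 27.1%.

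Above that value, perfect use looks worse. Take q = 20% as an illustration:
- p = 5%: period 1 is 1 − 0.80 × 0.698 = 44.1% against 40.1%, a gap of −4.0 points.
- p = 5% with ρ = 0.1-0.2: about −9 to −12 points.
- p = 10%, independent samples: 1 − 0.80 × 0.478 = 61.7% against 65.1%, a gap of +3.4 points.

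The sign therefore depends on rates that the SAP does not give.

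**The case against.** A reader might infer that the plan makes infringement periods look worse whenever there is no effect. The documents do not support that. V1_1 is inside the perfect-use window and is untreated, so the net bias can run either way. This limits the claim but does not rescue the test: the two distortions cancel only by accident. Removing V1_1 alone widens the count imbalance to about 7 versus 10.

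It may also be said that the size is modest. That stands in part. With V1_1 treated as on-drug, the excess at ρ = 0.1-0.2 is 2.5 to 5.4 points and the exact test stays near or below its nominal level. The three added samples fall on consecutive days and may be more strongly correlated than spaced visits, which would shrink the excess. The 14-15 points in Section 2.5 are a design difference, not a threshold for this endpoint.

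A further tempting argument is that the extra visits for a follicle of 15 mm or more add to the imbalance. They do not by themselves: the rule is the same in all three periods. If infringement led to more such follicles, the added samples would partly reflect a real effect.

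Finally, the study is exploratory and the endpoint secondary. The primary model and the subordinate primary analysis use fixed samples at R-1, R and R+1 and are not touched. That stands, and it limits the consequence.

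**Conclusion.** The point holds in limited form. Followed exactly, Section 3.7.2.1 compares a maximum over about 8 samples, one of them untreated, with a maximum over about 10, without adjustment. The comparison with perfect use is biased, and the net direction cannot be told from the SAP. Among on-drug samples alone the bias is against the infringement periods: 4 to 9 points at p = 5-10% and ρ = 0.1-0.2, or 10 to 13 points if samples are independent. The untreated sample can offset or reverse this. The sample counts follow from the schedule; p, ρ and q are assumptions. The defect should be corrected, but it does not threaten the primary results.

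**What to change.** - Exclude the pre-dose V1_1 sample from the perfect-use window.
- Base the test against perfect use on a quantity that does not grow with the number of samples: the per-visit probability of a score of 4 or less at scheduled on-drug visits, by GEE logistic regression with woman as cluster and period type as factor. Scheduled means the twice-weekly visits and the three delayed/missed-pill days, without follicle-triggered extras.
- Keep the worst score as description, with the number of samples per period printed beside it.
- Add a sensitivity analysis of the worst score over an equal number of on-drug visits per period, chosen by a rule fixed in advance.
- State whether the floor of 7 assessments counts V1_1. Without it, a woman on the regular schedule has 8 − 1 = 7 in period 1 and no margin for a missed visit.

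The cost is SAP wording and one model, with no new data. The downside is that a per-visit probability says less directly whether a woman lost protection at any time. It also dilutes a short loss around the infringement, which the subordinate primary analysis at R and R+1 already addresses. Leaving out the follicle-triggered visits sets aside samples taken near possible ovulation, so these should stay in the descriptive worst-score table.

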### 3.7.2.2 Ovarian activity in each type of treatment period

The aim of this secondary objective is to describe the distribution of the ovarian status among the subjects, during reported perfect use, during a treatment period with a delayed pill intake of 6 hours and during a treatment period with a missed pill of norgestrel 75 mcg. The adjudication committee will evaluate whether cycles should be excluded from analyses (including period 1 cycles if low compliance of taking study drug). The details for the review process will be defined in a separate document prepared for the adjudication process. The FASO population will be used for the analysis and a sensitivity analysis will be done using ITT and PP.

The time frames are:

- reported perfect use period: all the visits of the period 1
- delayed pill intake period: all the visits of the period 2 for Arm A and all the visits of period 3 for Arm B
- missed pill period: all the visits of the period 2 for Arm B and all the visits of period 3 for Arm A

The assessment criterion is the OS as defined in Appendix 5.4.

The OS are ranked depending on the risk of conception:  $OS_{nlp} > OS_{alp} > OS_a > OS_q$ . The OS classification will be determined by the adjudication committee.

For each treatment period the most risky OS will be considered.

The endpoints are:

- The percentage of subjects with  $OS_q$ ,  $OS_a$ ,  $OS_a/OS_{alp}$  and  $OS_{nlp}$  in reported perfect use period
- The percentage of subjects with  $OS_q$ ,  $OS_a$ ,  $OS_a/OS_{alp}$  and  $OS_{nlp}$  in delayed pill intake periods
- The percentage of subjects with  $OS_q$ ,  $OS_a$ ,  $OS_a/OS_{alp}$  and  $OS_{nlp}$  in missed pill periods
- The percentage of subjects with  $OS_{nlp}$  in all periods

A stratified McNemar test (stratification on the site, CMH option in SAS) will be used to compare the distribution of ovarian activity classification in the perfect use period to the delayed and missed pill periods (pairwise vs perfect use). The worst (meaning most risk of ovulation) ovarian activity category in the period will be used for the analyses.

